4.3. Required Evaluations/Management (baseline prior to initiation of any protocol treatment)

- a) Cystoscopic evaluation by the participating urologic surgeon no more than 6 weeks prior to registration will include bimanual examination under anesthesia, as thorough as possible, a transurethral resection of the bladder tumor. Patients referred from an outside hospital with a muscularis propria-invading bladder tumor will be re-resected by the participating urologist.
- b) Radiologic evaluation including chest CT, abdominal and pelvic CT and bone scan no more than 6 weeks prior to start of treatment.
- c) Comprehensive metabolic panel (CMP) obtained no more than 4-6 weeks prior to registration

5. Randomization

5.1 Radical Cystectomy Arm- Those randomized to “Radical Cystectomy” will be scheduled for surgery. In brief, radical cystectomy is the removal of the entire bladder, nearby lymph nodes (lymphadenectomy), part of the urethra, and nearby organs that may contain cancer cells. In men the prostate, the seminal vesicles, and part of the vas deferens are also removed. In women the cervix, the uterus, the ovaries, the fallopian tubes, and part of the vagina are also removed. Participants in this group may also undergo neoadjuvant chemotherapy prior to the surgery as is the current standard of care. The decision for specific chemotherapy regimen is based on medical oncologist’s evaluation. All AE occurring during the study period will be assessed and attribution assigned.

The surgical approach, robotic versus open, is determined by patient and surgeon mutual preference. All urinary diversions will be done via an open incision and the mode of diversion, whether intracorporeal or extracorporeal (orthotopic neobladder, continent cutaneous diversion or ileal conduit) will be selected by mutual agreement of the surgeon and patient, as is customarily done. The extent of the lymph node dissection will be determined by the surgeon but at minimum will include the external iliac, obturator, and hypogastric regions.

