5.3 DRUG THERAPY

Medical Oncologist will determine the chemotherapy regimen concurrently used with radiation as a radiation sensitizer. The following is a list of chemotherapeutic drugs that could be used per NCCN guideline:

Cisplatin

Cisplatin and 5-FU

5-FU and Mitomycin

Cisplatin and Paclitaxel

Low dose gemcitabine

All AE occur during the study period will be assessed and attribution assigned.

6. Post-Induction Response Evaluation (for Chemoradiation Arm only)

Following the completion of induction chemoradiotherapy and the evaluation of response all patients must be re-registered via cystoscopy and biopsy. At this time, the response results (biopsy results and cytology results) and the second phase of the treatment (i.e. radical cystectomy for tumor response $T \geq 1$ or consolidation chemoradiotherapy for tumor response T0, Ta, and Tcis) will be recorded and a new data collection calendar generated. Details regarding “Radical Cystectomy” can be found at Section 5.1. Details regarding “Consolidation Chemoradiotherapy” can be found at Section 5.2.2.

The following information will be supplied:

- original case number
- results of evaluation and pathologic T stage
- treatment start date (radical cystectomy or consolidation chemoradiotherapy)

The treatment option registered and the new data collection calendar will be based on the parameters specified by the protocol. If the investigator or the patient deviates from the protocol specified treatment, documentation of this and data submission as outlined in our study Standard operating procedure.

Patients who have developed distant metastases during the induction phase of treatment and who will not continue therapy will remain on the original calendar schedule for continued follow up only.

After completing either radical cystectomy or consolidation chemoradiotherapy, all response results to the second phase of treatment (i.e., either pathologic staging from the radical cystectomy or cystoscopic re-evaluation performed following completion of consolidation chemoradiotherapy) will be promptly submitted to Data Management.

7. 1 Post-Treatment Study Visits at 3, 6, 9, 12, 18, 24, 30, and 36 month \pm 1 month

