Post-treatment study visits will occur every three months (\pm 1 month) up to one year and every six months (\pm 1 month) thereafter up to two years (i.e. Months 18, 24, 30, and 36). These study visits will be scheduled during the same time as the participant's routine visit (i.e. standard of care) whenever possible. If not, study team member will work with participant on a time that is convenient. An imaging study either a CT abdomen and pelvis or MRI of abdomen and pelvis will be done as standard of care prior to the routine clinic visit. The treating physician will assess AE and assign attribution. Research study team member will coordinate with the participant to meet either before or after the routine clinic visit. Participants will be asked to complete study questionnaires. The questionnaires may also be mailed and/or emailed back to the study team if they cannot be completed within the allotted study time. And those randomized to "chemoradiation Group" will also undergo routine cystoscopy during these follow-up visits (SOC).

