8.2 CHEMORADIATION ARM

	Initial Visit	Pre-Treatment (tx) TURBT	Baseline	Treatment Period: Chemoradiation	Post-Induction Response Evaluation with Cystoscopy and biopsy (3-4 weeks following Induction Chemoradiotherapy) and second phase of treatment**	Post-tx 3 mon f/u ± 1 mon	Post-tx 6 mon f/u ± 1 mon	Post-tx 9 mon f/u ± 1 mon	Post-tx 12 mon f/u ± 1 mon	Post-tx 18 mon f/u ± 1 mon	Post-tx 24 mon f/u ± 1 mon	Post-tx 30 mon f/u ± 1 mon	Post-tx 36 mon f/u ± 1 mon (end of study visit??)			
Study eligibility	X		X													
Informed consent	X															
Assessment of AE								X	X	X	X	X	X	X	X	X
SOC Image studies (X-Ray, CT, and/or MRI)			X					X	X	X	X	X	X	X	X	X
Radiation & Medical Oncology Consults (SOC)			X													
Research blood sample			X					X	X	X	X	X	X	X	X	X
Ht, Wt, and Vitals [#]			X					X	X	X	X	X	X	X	X	X
Research Study Questionnaires			X					X	X	X	X	X*	X*	X*	X*	X*

Note:

SOC = Standard of Care

information may be extracted from EMR

*Research study questionnaire may be emailed or mailed per patient's stated preference

** Post-treatment cystoscopy is SOC for chemoradiation patients ONLY

**Pending on the results of post-induction TURBT and response evaluation, participant may receive further treatments. Details on the second phase of treatment are listed in Section 6 and Study Synopsis.

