9. DATA COLLECTION & STUDY EVALUATIONS

Medical records will be reviewed prior to “Baseline Study Visit” to confirm study eligibility. After obtaining consent, socio-demographic data will be collected through chart review and interviews. Clinical data that will be collected include but not limited to bladder cancer treatment history, tumor characteristics, stage, laboratory results, medications and co-morbidity.

Study team member or clinic staff will measure height, weight, and vital signs at each specific study time point. Research blood will be drawn at each study time point. Blood and tissue samples may be banked under the optional study (HSC20050234H GU Tissue Bank). For those participants who declined to participate in the optional study, any leftover samples will be permanently de-identified through the GU Tissue Bank (HSC20050234H) honest broker system. At the close of this study, all biological materials collected will be rolled into HSC20050234 GU Tissue Bank.

9.1 Feasibility: We will report recruitment, visit dates, adherence, attrition rates and compliance with randomization for each arm of the study

9.2 Bladder-intact survival: We will report proportion of patients who failed chemoradiation and required salvage cystectomy

9.3 Quality of life: A self-assessment questionnaire using the European Organization for Research and Treatment of Cancer (EORTC) QLQ- C30 and FACT-Bladder will be used for QOL assessment at baseline, 3, 6, 9 and 12 months.⁸

9.4 Progression free survival: This will be measured from the date of finishing chemoradiation or radical cystectomy to the date of first documentation of progression. Progression will be determined using RECIST 1.1 criteria by the treating physician based on radiographic or pathologic evidence of disease progression, or death from disease. Any documented recurrence will be considered progression.⁹ The date of progression will be recorded.

9.5 Candidate gene expression analysis: For the participants who have consented to be part of the optional study (“GU Tissue Bank HSC20050234H), a microarray analysis will be performed on all bladder tumor specimens using Agilent Technologies (Agilent SurePrint G3 Human Gene Expression 8x60K v2) Microarray. Goal is to study the landscape of 50 important candidate genes, which are involved in bladder cancer (for example-BRAF, KRAS, EGFR, FGFR).

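### PFS counts non-muscle-invasive bladder recurrence, an event open only to chemoradiation patients who keep a bladder; add a supporting PFS analysis on invasive and metastatic failure

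*Combined protocol and SAP*

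**What the plan says.** All references are to the combined protocol and SAP.

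- **Event.** Section 9.4 has progression determined under RECIST 1.1 "by the treating physician based on radiographic or pathologic evidence of disease progression, or death from disease". It adds: "Any documented recurrence will be considered progression". Pathologic evidence is accepted, so a positive bladder biopsy qualifies.
- **Time origin.** Also in 9.4: "This will be measured from the date of finishing chemoradiation or radical cystectomy to the date of first documentation of progression".
- **Cystectomy arm.** Section 5.1: "radical cystectomy is the removal of the entire bladder, nearby lymph nodes (lymphadenectomy), part of the urethra".
- **Chemoradiation arm.** Section 6 sends post-induction T1 or higher to cystectomy. It provides "consolidation chemoradiotherapy for tumor response T0, Ta, and Tcis", and these patients keep the bladder.
- **Surveillance.** Section 7.1 gives abdominal and pelvic imaging without distinction by arm, and routine cystoscopy to the chemoradiation group. A note to the calendar in 8.2 reads: "Post-treatment cystoscopy is SOC for chemoradiation patients ONLY".
- **Analysis.** Section 11 tests non-inferiority of chemoradiation on PFS with a logrank test. It gives no PFS rate, margin, hazard ratio or event count.

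**The concern.** PFS is compared between an arm in which every patient has lost the bladder and an arm in which many keep it. A new superficial tumour in a retained bladder ends progression-free time in the second arm and has no counterpart in the first.

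The protocol itself treats invasion as the dividing line elsewhere: section 1 ties salvage cystectomy to invasive recurrence. Section 9.4 makes no such distinction. If invasive and metastatic control were the same in both arms, the extra event type would still lower the chemoradiation curve. A reader could then take the gap for worse control of the disease that threatens life.

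The trial is a 30-patient pilot, so the main stake is interpretation and carry-forward. Aim 2b is about the feasibility of a powered trial of the same design, which could inherit the definition.

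**Working it through.** **Step 1. Which PFS events can each arm have?**

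| Event under 9.4 | Cystectomy | Chemoradiation |
|---|---|---|
| Distant recurrence | yes | yes |
| Pelvic recurrence, soft-tissue or nodal | yes | yes |
| Death from disease | yes | yes |
| Muscle-invasive bladder recurrence | no | yes, if bladder retained |
| Non-muscle-invasive bladder recurrence | no | yes, if bladder retained |

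The last two rows are open to one arm only. Muscle-invasive recurrence is a plain failure of treatment. Non-muscle-invasive recurrence is the row that can separate PFS from invasive and metastatic control.

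**Step 2. Does anything else in the plan remove that row from PFS?** No. Section 9.2 reports the proportion who failed chemoradiation and needed salvage cystectomy, and section 11 analyses bladder-intact survival. Neither alters the PFS event in 9.4.

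**Step 3. How large could the effect be?** There is no PFS figure in the plan to reproduce; the only sample size, 171 per group, is for quality of life. The following is an illustration on assumed inputs:

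- S = 0.60, three-year PFS on all other event types, equal in both arms (assumed).
- b = 0.10 to 0.30, three-year risk of non-muscle-invasive bladder recurrence in the chemoradiation arm, independent of the other events (assumed).
- n = 15 per arm (section 3.3).

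Observed chemoradiation PFS = S × (1 − b):

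- b = 0.10: 0.60 × 0.90 = 0.54, which is 6 points below 0.60.
- b = 0.30: 0.60 × 0.70 = 0.42, which is 18 points below 0.60.

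In patients: 15 × 0.06 = 0.9 and 15 × 0.18 = 2.7, or about 1 to 3 of 15.

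With constant hazards, the hazard ratio is ln(S × (1 − b)) / ln(S):

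- b = 0.10: ln 0.54 / ln 0.60 = 1.21.
- b = 0.30: ln 0.42 / ln 0.60 = 1.70.

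The value on the shared events is 1.00. Letting S run over 0.50 to 0.74 with the same b widens the hazard ratio to 1.15 to 2.18, and the difference to 5.0 to 22.2 points. These ends of the range for S are also assumptions. Section 1.1.1 gives 74% and 50%, but as disease-specific survival by response, so they serve only as a bracket.

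**Step 4. Is there a push the other way?** Yes. Tumour of T1 or higher after induction is a local failure seen before treatment is complete. Since the 9.4 clock starts at completion, that finding is not a PFS event, which favours chemoradiation. The documents give no rate for it, so the two effects cannot be netted.

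**The case against.** The strongest case is that counting every recurrence is a legitimate choice. A tumour in a retained bladder is a real consequence of keeping the bladder, not something missed in the other arm. Sections 1 and 11 state the hypothesis in terms of PFS, not invasive or metastatic control. The assumed effect is also small beside the noise: with 15 per arm and 60% PFS, the 95% half-width for a difference is 1.96 × √(2 × 0.6 × 0.4 / 15) = 0.35, or about 35 points. Bladder-intact survival is analysed as well.

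Most of this stands, and it is why the 9.4 definition should be kept. It does not show that PFS as defined can be read as invasive and metastatic control, and no other planned result supplies that reading.

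Two stronger inferences are tempting and not supported:

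- *That sections 6 and 9.4 contradict each other on Ta and Tcis.* Section 6 directs treatment for residual tumour after induction; 9.4 concerns findings after treatment has finished. The time points differ, so there is no contradiction.
- *That the one-arm event is a detection artefact.* Cystectomy patients cannot have a bladder recurrence, so none goes undetected in that arm.

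**Conclusion.** The point holds in limited form. As written, PFS includes non-muscle-invasive bladder recurrence, which only chemoradiation patients with a retained bladder can have. Taken alone, this works against chemoradiation and makes non-inferiority harder to show, not falsely easy.

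The size, 54% to 42% against 60%, rests wholly on the assumed 60%, the assumed 10% to 30%, and independence. It is not an estimate for this trial.

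A reader might infer that the PFS result is bound to be biased against chemoradiation, or that it cannot answer the stated hypothesis. The documents support neither. Uncounted post-induction failure pulls the other way, and PFS as defined does address a hypothesis stated as PFS. What is missing is a planned result that lets invasive and metastatic failure be read separately.

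**What to change.** Keep the 9.4 definition and add to section 11 one pre-specified supporting PFS analysis:

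- Use the same time origin and the same death rule as 9.4, so that the two results differ only in which recurrences count.
- Count muscle-invasive bladder recurrence, pelvic recurrence (soft-tissue or nodal) and distant recurrence. Do not count non-muscle-invasive bladder recurrence.
- State in advance how a T1 bladder recurrence counts.
- Report non-muscle-invasive bladder recurrence separately in the chemoradiation arm.
- Call it a comparison on invasive and metastatic failure. It is not strictly like-for-like, because invasive bladder recurrence also needs a retained bladder.

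The cost is one extra analysis and a second PFS result to present. For progression, section 9.4 promises only the date, so site and stage of each recurrence should become explicit data fields. Existing pathology and imaging reports should supply them.

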2. HYPOTHESIS AND SPECIFIC AIMS

Multiple prospective radiation therapy protocols have evaluated bladder-preserving chemoradiation therapy approach for muscle-invasive bladder cancer (MIBC), with radical cystectomy reserved for radiation failure. Aims of bladder preservation in MIBC are to offer a quality-of-life advantage and avoid potential morbidity or mortality of RC without compromising oncologic outcomes. Because of lack of level-1 evidence, oncologic equivalence of bladder preservation modality treatments compared with RC remains unknown.

2.1 HYPOTHESIS:

We hypothesized that chemoradiation is non-inferior to radical cystectomy for treatment of MIBC.

2.2 SPECIFIC AIMS:

SPECIFIC AIM 1a To determine and quantify quality of life in patients treated with radical cystectomy and chemo radiation therapy

1b To determine and quantify progression free survival and bladder-intact survival in patients treated with radical cystectomy and chemoradiation therapy,

SPECIFIC AIM 2a To evaluate genetic markers predicting response to chemoradiation by performing tissue RNA microarrays.

2b To assess the feasibility of conducting an adequately powered non-inferiority trial of the same design via recruitment rate, patient adherence to both treatment arm, and attrition.

2.3 STUDY DESIGN:

Our study will be a pilot, prospective, single-center, randomized non-inferiority trial comparing chemoradiation therapy to radical cystectomy. Patients diagnosed with muscle invasive bladder cancer after transurethral resection of bladder tumor and are surgical candidates will be randomized to either radical cystectomy (with neoadjuvant chemotherapy if suitable candidate) or chemoradiation.

Both treatment methods are considered “standard of care” recommended by the NCCN Clinical Practice Guidelines (http://www.nccn.org/professionals/physician_gls/pdf/bladder.pdf) in treating muscle invasive bladder cancer.

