9.6 Activities of Daily Living (ADL) scores: This will be measured at baseline, and during all subsequent follow-up visit (i.e. 3, 6, 9 And 12 months) using Activities of Daily Living QOL Questionnaire using Katz Index of Independence in Activities of Daily Living (ADL).¹⁰

9.7 Retrospective screening & chart review: We will screen and review charts of “potential participant” retrospectively using the latest approved eligibility criteria and study schema to determine:

1. the number of “would-be potential participants”
2. the number of those who were initially deemed eligible and was truly eligible after TURBT
3. the number of those who were initially deemed eligible but was ultimately ineligible after TURBT

4. rationale for ineligibility

The retrospective screen & chart review will start from the date when the study was first approved by the IRB (i.e. April 15, 2016) until present time. Data including but not limited to medical record number, initials of name, gender, race, ethnicity, TURBT result, age at time of treatment, treatment received, date of treatment, eligibility status for the study, and rationale if deemed ineligible, will be captured. We do not intend to contact these patients for study enrollment since they would've received treatments for their diagnosis already. Our intention for this retrospective data collection is that it will provide further insight and information on the potentiality of chemoradiation as treatment modality for patients with specific bladder cancer diagnosis. We need to capture this data in order to represent total population of patients screened, thereby determining the denominator of the study population.

9. 8 Outline of Captured Data

Outcome of Interest	Measure	Method of Assessment
Demographics		Self-report questionnaire
Health History including height, weight, and vital signs		Physical exam, review of EPIC
Study Processes		
recruitment rate adherence attrition feasibility bladder intact survival safety		
Outcomes of interest		
Quality of Life	EORTC	Self-report questionnaire
	FACT-BI	Self-report questionnaire
ADL	Katz ADL	Self-report questionnaire
Progression free survival	RECIST 1.1	Physician assessment
Candidate gene expression	Candidate genes	Laboratory analysis of blood and tissue

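### Aim 2a seeks markers that predict chemoradiation response, but no section limits the predictor to a pre-treatment sample or to one specimen per patient

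*Combined protocol and SAP*

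**What the plan says.** Aim 2a (Section 2.2) is "To evaluate genetic markers predicting response to chemoradiation by performing tissue RNA microarrays". Section 1 gives the purpose: such markers would let patients be directed to the treatment most likely to help them.

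The assay is described in Section 9.5. It applies to tissue-bank consenters ("For the participants who have consented to be part of the optional study"), and for them "a microarray analysis will be performed on all bladder tumor specimens using Agilent Technologies". The scope is stated as "Goal is to study the landscape of 50 important candidate genes". No sampling time is given.

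Tumor tissue can arise at several points:
- the TURBT before randomisation (Section 4.1, which also describes banking of leftover TURBT tissue);
- the evaluation after induction, where "all patients must be re-registered via cystoscopy and biopsy" (Section 6);
- cystectomy after induction, which Section 6 assigns to patients with T1 or higher;
- cystectomy in the surgical arm, where "Participants in this group may also undergo neoadjuvant chemotherapy prior to the surgery as is the current standard of care" (Section 5.1).

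On blood, Section 9 states "Research blood will be drawn at each study time point", and the gene-expression row of Section 9.8 reads "Laboratory analysis of blood and tissue". Section 11 compares biomarkers between treatment arms by t-test or Wilcoxon test and fits a logistic model for treatment arm. It names no specimen, no time point and no handling of repeat specimens.

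**The concern.** A marker used to choose between cystectomy and chemoradiation is read before either begins. Expression measured after 40 Gy with chemotherapy, or after neoadjuvant chemotherapy, reflects the treatment as well as the tumor's starting biology. If such specimens enter the predictor, a gene that merely moves under treatment can look like a marker of non-response, or like a difference between arms.

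The supply of later specimens is also tied to the outcome. A T0 patient has no post-induction tumor to profile, and a post-induction cystectomy specimen is prescribed only for T1 or higher. Patients who respond poorly can therefore contribute more arrays, and more treatment-exposed arrays, than those who respond well. If repeat specimens were treated as independent, the test would overstate its information even for a gene that treatment leaves unchanged.

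At stake is whether the marker results could be used for the pre-treatment selection that Section 1 has in mind.

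**Working it through.** **Reading the sections together.** The plan states no sample size, power or alpha for Aim 2a, so there is no figure to reproduce. Three questions settle the textual point.

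1. Does any section restrict the assay to pre-treatment tissue? Section 9.5 does not. Section 4.1 describes banking of TURBT leftovers but does not confine the assay to them. Section 9 says more generally that blood and tissue may be banked and that all collected material goes to the bank at study close.
2. Does any section restrict the analysis to one specimen per patient? Sections 9.5, 9.8 and 11 do not.
3. Does the availability of later tumor depend on response? Section 6 sends T1 or higher to cystectomy and T0, Ta and Tcis to consolidation, while Section 5.2 gives consolidation to complete responders. T0 patients have no tumor to assay. Ta and Tcis patients have residual tumor but are handled as responders. Availability depends on response without being confined to non-responders.

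**Scale (illustration only).** The documents give the chemoradiation arm of 15 (Section 3.3) and the 50 genes (Section 9.5). The assumptions are:
- all 15 patients banked;
- 11 responders and 4 non-responders, loosely from the figure of more than 70% in Section 1 (11/15 = 73%);
- unit variance and within-patient correlation 0.5;
- no true pre-treatment difference;
- two-sided t-test at 0.05, responders versus non-responders, each specimen counted as independent;
- treatment shifts post-treatment expression by *d* SD.

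The bias in the difference of means follows directly:
- Non-responders with 4 pre-treatment specimens and 4 biopsies: (4/8)*d* = 0.50*d*.
- With 4 cystectomy specimens added: (8/12)*d* = 0.67*d*.
- If 2 responders also give Ta/Tcis tumor, the responder mean moves by (2/13)*d* = 0.15*d*. The biases fall to 0.35*d* and 0.51*d*.

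Simulated per-gene false-positive rates (20,000 replicates per setting; Monte Carlo standard error at most √(0.25/20,000) ≈ 0.4 percentage points):

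| Specimens entering the test | *d* = 0.5 | *d* = 1.0 | *d* = 1.5 |
|---|---|---|---|
| Pre-treatment only, one per patient | 5% | 5% | 5% |
| Plus biopsies, non-responders only | 11% | 19% | 28% |
| Plus biopsies, 2 Ta/Tcis responders contribute | 10% | 13% | 15% |
| Plus biopsies and cystectomy, non-responders only | 17% | 34% | 54% |
| Plus biopsies and cystectomy, 2 Ta/Tcis responders contribute | 16% | 25% | 36% |

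With *d* = 0 the pooled rates are still about 9–12%. That part comes from repeat counting alone.

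Varying the number of non-responders from 3 to 6 changes little. With biopsies pooled and *d* = 1, the rate is 17–19%, or 12–13% if 2 responders contribute.

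If all 50 genes were null and all shifted equally, 5% is 2.5 false leads, 10–28% is 5 to 14, and 16–54% is 8 to 27.

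**The analysis actually planned.** Section 11 compares arms. Because arms are randomised, pre-treatment expression should differ between them only by chance. A systematic arm difference would have to come from treatment-exposed specimens, such as surgical tissue after neoadjuvant chemotherapy. An arm comparison therefore cannot identify predictors of response, whichever specimens are used.

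**The case against.** The strongest reply is that pooling is nowhere planned. Section 9.5 says what is assayed, not what is combined, and the banking text in Section 4.1 points to TURBT tissue as the likely source. This stands: the defect is an unspecified predictor, not a stated intention to mix. It does not remove the point, because Section 9.5 covers all specimens and an analyst following it could pool without departing from the plan.

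A reader might infer that post-induction tumor exists only in non-responders. The documents do not support that, since Ta and Tcis patients go to consolidation. Allowing for them lowers the illustrated rates.

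A reader might also infer that serial blood will be used as a predictor. Aim 2a and Section 9.5 concern tissue. Blood appears for gene expression only in one cell of Section 9.8, with no assay, time point or analysis. What remains is an inconsistency to resolve.

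Finally, the simulated test is not in Section 11, so its rates are not error rates of the planned analysis. Section 1 gives a responder versus non-responder comparison as the goal, with cystectomy as a reference, but no section turns it into a test. Nor do the documents say that a marker list will be carried into the larger trial; Section 1 describes the pilot's contribution as feasibility data.

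**Conclusion.** The point holds as a gap in specification. Aim 2a needs a pre-treatment measurement, and Sections 9.5, 9.8 and 11 leave open both the time point and the number of specimens per patient. Read literally, they admit treatment-exposed tumor whose availability depends on the response to be predicted.

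The direction of the resulting error is clear. Its size is not known from the documents. The illustrated rises from 5% rest on assumed shift sizes, correlation, response split and full banking consent, and part of each rise is repeat counting. The upper ends (28% and 54%) require a 1.5 SD shift and no tumor from Ta/Tcis responders.

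Correcting the specimen alone would not deliver Aim 2a, because Section 11 models treatment arm rather than response. The change should be made: it costs little, and without it the marker aim may not be interpretable. It does not affect the trial's treatment comparison.

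**What to change.** State in Sections 9.5, 9.8 and 11:
- The Aim 2a predictor is expression in one specimen per patient, the pre-randomisation TURBT that contains tumor.
- If blood is assayed, only the baseline draw is used as a predictor. Otherwise remove blood from the gene-expression row of Section 9.8.
- Post-induction, cystectomy and follow-up samples are not predictors. They are reported separately as within-patient change from baseline.
- The outcome for this predictor is post-induction response within the chemoradiation arm. Define response for the analysis and say explicitly how Ta and Tcis are classed, since Sections 5.2 and 6 describe the groups in different terms.

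This is protocol and analysis wording; it adds no visit or procedure and changes no care. Fewer arrays enter the predictor analysis. Patients whose study TURBT contains no tumor drop out of it unless an existing outside block is available. That could happen after the re-resection that Section 4.3 requires for referred patients. Section 4.1 does not describe use of outside blocks, so that source would need to be covered explicitly.
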